5.1.8 Safety Analysis

The following variables will be evaluated to assess the safety:

- Adverse Events
- Vital Sign.
- Physical Examination

5.1.8.1 Adverse Events (AE)

All verbatim AE terms will be coded using the MedDRA (version 24.1), listed and summarized by SOC and PT for Safety Population by treatment group and overall.

Treatment-Emergent Adverse Events (TEAEs) will be defined as AEs not present prior to the first patch application (FIRTECH Patch) or randomization (No Patch), or AEs present before that worsened after the first patch application (FIRTECH Patch) or randomization (No Patch). If a partially missing date of onset allows the possibility that an AE may be a TEAE it will be presumed to be a TEAE. Unanticipated Adverse Device Effect (UADE) will be defined as any serious TEAE related to the study device.

TEAEs will be analysed by treatment group and overall. UAED will be analysed only for FIRTECH Patch treatment group.

AEs will be summarized by treatment group and overall by the number and percentage of subjects who experienced at least one AE of any of the following types: any AE, any TEAE, any device-related

CONFIDENTIAL Page 24 of 30

Study No LPS16453 Date: DEC 12, 2022

Private and Confidential

TEAE, any serious TEAEs, any UADE, any SAE leading to death, any TEAE leading to study discontinuation, any serious TEAEs leading to study discontinuation.

TEAEs will be summarized by the highest relationship to study device (Related or Not Related) and maximum severity (Mild, Moderate, Severe). If the relationship of AE or TEAE to the study device is unknown, then the event will be classified as Related.

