7.6 Clinical Procedures

The study will be performed in Investigational Sites and an online e-diary will be used.

A total of 2 site visits and 1 phone contact are planned during a maximum of 5 days of treatment and 6 days of total study duration.

7.6.1 Day 1, Visit 1

Clinical procedures on Day 1, Visit 1 include the following:

- Verification of eligibility
- Informed Consent Signatures
- Local Physical Examination

- Collection of Vital Signs to include: Respiratory rate, Heart rate, Temperature, Blood Pressure
- Collection of Demographics to include: Age, Gender
- Collection of relevant medical history and concomitant medications
- On-line daily e-diary will be explained and activated
- Urine pregnancy testing (for women of childbearing potential only)
- Causes and/or circumstances triggering the acute back pain
- Baseline Subject symptom self-assessment
 - Pain Perception (NRS): Numerical Rating Scale^[3] for pain assessments at baseline and at defined time points: 0-10 NRS; '0' representing "no pain" and '10' representing "worst pain imaginable
 - Instantaneous: pain at the moment of the evaluation
 - Average pain in the previous 12 hours.
 - Worst pain in the previous 12 hours
 - Least pain in the previous 12 hours
 - o Roland-Morris Disability Questionnaire (RMDQ)^[5]
- Baseline mobility assessment (physician)
- Randomization:
 - O Arm A: ITP FIRTECH: Patch application according to the instruction for use in Section 17.3: The patch has to stay in position for 5 days. If the patch is taken-off or if it fell off during the study duration, the subject is invited to replace the patch at home following the instruction for use. Subject is allowed to take-off the patch at any time in case of severe skin itchiness, irritation, or skin reaction and in this case the subject has to contact the study center.
 - o Arm B: no-patch: Subjects will be informed that they will not be assigned a patch in this study.
- All subjects are informed that rescue mediation (paracetamol, up to 2 g per day), while not encouraged, is allowed if necessary.
- All subjects will be informed of the prohibited medications.
- If rescue medication is taken, the exact moment(s) and the dose(s) have to be indicated in the e-diary.
- An explanation will be provided on how to use e-diary at home and providing all necessary access credentials
- All subjects will be requested to avoid bed rest and will be recommended to continue with a normal daily life activity.

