9.3 Anticipated Adverse Events

No Serious Adverse Events are anticipated for this trial. Anticipated adverse events include minor skin irritation at the site of patch application as described above. The frequency of occurrence of skin irritation is unknown.

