In case the first patch falls off, apply the second patch to the same area, closely following the instructions again.

Recommendations:

- The patch is water-resistant, which means that it remains active even when it is wet. You can shower with it. After you shower, gently pat the patch dry with a towel without rubbing.
- Avoid very hot water, sauna, steam bath, bathing or swimming, as this can cause the patch to peel off.
- Avoid to wear tight clothes that can increase the risk of the patch peeling off.
- Avoid to apply any oily substance on the patch area during the time when you are wearing the patch

How to peel off the patch on Day 5:

Remove the patch by gently lifting one end and dispose as household waste. Do not reuse..

Warnings

- Store at room temperature.
- For external use only.
- Apply only to clean, dry, undamaged skin.
- Discontinue treatment in the event of evident irritation or hypersensitivity to the product.
- In case of specific blood circulation or muscular problems, seek the advice of your doctor before applying the plasters.
- Keep out of the reach of children.
- The patch should only be used by adults (> 18 years old).
- Do not use if the packaging is broken or punctured since damaged packaging could compromise efficacy and safety of the product
- Should not be used for pregnant or lactating women
- (Read the instructions for use)

SIGNATURE PAGE

IRPATCH Study #LPS16453; Version 4 / 22 Jul 2022

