5.1.7.5.2 Patch Use Compliance

Patch use compliance will be measured based on the number of days the subject wears a FIRTECH patch without reapplication (duration of wearing the patch after the first application till the first removal). Subject will be considered as patch use compliant if the first patch is worn at least for 4 days. Otherwise, subject will be considered as non-compliant.

The number and percentage of compliant and non-compliant subjects will be presented along with descriptive summary of Patch Use Compliance (Days) and number and percentage of subjects from following Patch Use Compliance categories:

• 1 day;

• 3 days;

• 5 days;

• 2 days;

• 4 days;

• > 5 days.

Summary of patch use compliance will be based on the Safety population.

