5.1.8.3 Physical Examination

The physical examination will be listed and summarized for the Safety population by treatment group and overall by the number and percentage of subjects with abnormalities of the spine (lumbar lordosis, scoliosis, kyphosis, other), asymmetry and integumentary findings on the lower back (mole, scar, birth mark, discolouration, other) by visit (Baseline Visit 1 and Day 5 Visit 2).

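### The SAP tabulates adverse events that end study participation but not those that lead to patch removal, so no specified summary shows how many patch users stopped the device for a skin reaction

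*SAP*

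**What the plan says.** **Adverse-event overview (SAP 5.1.8.1, Table 14.3.1.1).** The rows begin with "any AE, any TEAE, any device-related" TEAE, continue through serious TEAEs and unanticipated device effects, and end with "any SAE leading to death, any TEAE leading to study discontinuation" and the serious subset of the latter. TEAEs are also tabulated by system organ class and preferred term, by maximum severity and by relationship. An unknown relationship is classed as related.

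**Removal of the patch (Protocol 7.6.1).** "Subject is allowed to take-off the patch at any time in case of severe skin itchiness, irritation, or skin reaction"; the subject must then contact the centre. Section 9.2.1 names removal as the way the skin risk is mitigated.

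**Anticipated harm (Protocol 9.3).** Minor irritation at the application site is the only event named, and "The frequency of occurrence of skin irritation is unknown".

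**Patch-use compliance (SAP 5.1.7.5.2).** A shorter wear of the first patch makes the subject non-compliant; the rule begins "Subject will be considered as patch use compliant if the first patch is worn at least for 4 days. Otherwise, subject will be considered as". No exception or breakdown by reason is given.

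**Skin findings (SAP 5.1.8.3).** The examination summary covers "integumentary findings on the lower back (mole, scar, birth mark, discolouration, other") at baseline and at Day 5.

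**Tolerability.** The protocol synopsis promises a tolerability summary on the as-treated basis.

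**The concern.** Stopping the device and leaving the study are different events in this trial. With five days of wear, a Day 5 visit and a Day 6 call, a subject who peels the patch off on Day 2 because of itching has little reason to withdraw, and the protocol does not ask for withdrawal. The SAP's discontinuation rows follow study exit only, and the disposition summary (SAP 5.1.1) likewise gives reasons for study discontinuation only.

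For an adhesive patch whose one named anticipated harm is skin irritation, the share of users who had to take it off for that reason is the main tolerability result. As specified, the report could show few or no discontinuations due to adverse events while some patch users had stopped the device for one. Those users might be visible only within an undivided non-compliance count.

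**Working it through.** **1. Does removing the patch for a skin reaction lead to study exit?**

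| Source | Rule | Does early removal trigger exit? |
|---|---|---|
| Protocol 7.6.1, Table 3 note | Removal for a skin or safety reason is allowed; the centre must be contacted | No exit stated |
| Protocol 6.4.7, criterion 3 | Exit for non-compliance as defined in 7.9 | No: 7.9 covers e-diary entries and visits only |
| Protocol 6.4.7, criterion 4 | Exit if the investigator considers continuing harmful to the subject's well-being | Only by investigator judgement |
| Protocol 6.4.7, criterion 5 | Exit if an adverse event leads to withdrawal by the subject or on investigator judgement | Only if one of them decides so |

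So a subject can remove the patch for a reaction and remain in the study to Day 5. This is inferred from reading the rules together; no sentence states it directly.

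**2. Where does that subject appear in the planned output?**

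| Output | Contribution |
|---|---|
| Any AE, any TEAE, tables by class and term, severity and relationship | Counted once the reaction is reported |
| Device-related TEAE | Counted if judged related or of unknown relationship |
| TEAE leading to study discontinuation, and serious subset | 0 |
| Reasons for study discontinuation (SAP 5.1.1) | 0 |
| Patch-use non-compliance | 1 if the first removal is before 4 days, otherwise 0; no reason required |

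The event is therefore reported, but its consequence for treatment is not. The non-compliance count cannot stand in for it. It omits subjects who remove the patch for a reaction at 4 days or later. It also includes subjects whose first patch simply fell off, because the SAP counts wear of the first patch up to first removal. Protocol 8.3.1.4.2 counts days wearing a patch; SAP 5.1.11 does not list this change.

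**3. Denominator.** The plan's own figure reproduces: 180 / (1 − 0.10) = 200 randomized. At 1:1 this is 200 / 2 = 100 in the patch arm.

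**4. Illustration.** The documents give no rate of irritation, so the counts are assumptions. Let k of 100 patch subjects remove the patch for a skin reaction, all of whom attend Day 5. The study-discontinuation row shows 0/100 for every k. Its exact (Clopper-Pearson) upper limit is 1 − 0.025^(1/100) = 0.036.

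| Assumed k | Planned row (95% CI) | Removal because of an AE (exact 95% CI) |
|---|---|---|
| 5 | 0% (0 to 3.6%) | 5% (1.6 to 11.3%) |
| 10 | 0% (0 to 3.6%) | 10% (4.9 to 17.6%) |

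The chance of at least one such subject among 100 is 1 − (1 − p)^100, where p is the true probability of removal: 63% at p = 1%, 95% at 3% and 99% at 5%. Even a low removal rate would probably leave at least one subject to report.

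**5. Is the reason for removal recorded?** Yes, in the e-diary (Protocol 7.6.2, Table 3 note). SAP 3.4 says that e-diary data on patch application are transcribed to the CRF and that the CRF version is analysed. It does not say whether the reason for removal is transcribed too.

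**The case against.** The strongest reply is that the harm is not hidden. A reported skin reaction appears by arm as a TEAE, usually as device-related, and again by severity and by preferred term. The stated safety endpoints are incidences of adverse events, serious events and TEAEs, and all are reported. This stands. A reader might infer that the SAP counts only events leading to study discontinuation, or that the harm turns into non-compliance. Neither is supported: one attribute of the event is missing, not the event.

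A reader might also infer that the Day 5 examination cannot show irritation. That goes too far: the listed categories include discolouration, which could capture redness, and findings are tabulated at both visits. Irritation has no category of its own, but this is secondary. Nor is the skin check confined to scheduled removal, since Protocol 9.2.1 also covers early removal. A separate row for application-site skin TEAEs would largely repeat the class-and-term table.

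The zero in the illustration is a possible result, not an expected one. A subject with a reaction may withdraw, or be withdrawn, under exit criterion 5 and would then be counted.

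Finally, Table 14.1.3.1 or Listing 16.2.5 may already show reasons for removal; the mock-ups are not in the documents. The SAP text does not require it, however, and a subject-level listing is not a summary.

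**Conclusion.** The point holds for the discontinuation rows and the compliance table. No specified summary reports how many patch users stopped the device because of an adverse event, although the protocol allows this without study exit and promises a tolerability summary. The size depends on a removal rate that the documents do not give: under the assumption of 5 removals among about 100 patch subjects, all attending Day 5, the plan shows 0% where the tolerability result is 5% (1.6 to 11.3%). If some of those subjects withdrew, the gap would be smaller.

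It would be too strong to conclude that the overall tolerability picture must come out too favourable, because device-related TEAEs are still reported by severity. No test, efficacy result or stated endpoint changes. This is a gap in safety reporting that is worth closing because it is cheap to close.

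**What to change.** 1. In SAP 5.1.8.1 and Table 14.3.1.1, add for the FIRTECH group a row for any TEAE leading to patch removal, divided into permanent and temporary (patch replaced).
2. In SAP 5.1.7.5.2 and Table 14.1.3.1, split non-compliance by reason for first removal: adverse event, fell off, other.
3. First confirm that the reason recorded in the e-diary is transcribed to the CRF with the patch application data, and that a removal can be linked to an adverse event record. If the reason is not transcribed, SAP 3.4 needs an exception so that the e-diary entry can be used.

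The cost is a few table rows and the check in step 3. The downside is a safety summary that may look slightly less favourable.

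Separately, the patient instructions in Protocol 17.3 say for Day 5 "Remove the patch by gently lifting one end and dispose as household waste", whereas 4.4 and 7.6.3 have the patch removed at the site and used patches collected there. These passages contradict each other and must be reconciled; which of them governs is for the sponsor to settle. This does not affect how early removals are tabulated.

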5.1.8.2 Vital Signs

Vital signs, including measurements of respiratory rate (breathes per minute), heart rate (beats per minute), temperature (Celsius), systolic and diastolic blood pressure (mmHg), will be listed and summarized for actual values and change from baseline with descriptive statistics for Safety population by treatment group and by visit (Baseline Visit 1 and Day 5 Visit 2).

5.1.8.3 Physical Examination

The physical examination will be listed and summarized for the Safety population by treatment group and overall by the number and percentage of subjects with abnormalities of the spine (lumbar lordosis, scoliosis, kyphosis, other), asymmetry and integumentary findings on the lower back (mole, scar, birth mark, discolouration, other) by visit (Baseline Visit 1 and Day 5 Visit 2).

5.1.9 Subgroup Analyses

No Subgroup analyses will be conducted in this trial.

5.1.10 Interim Analysis

No Interim analyses will be conducted in this trial.

5.1.11 Changes to Analyses Specified in Protocol

The following changes have been made to analyses specified in the protocol:

- It was specified by the protocol to use the randomization time as the starting point for time-toevent endpoints. But exact time (hours) of randomization is not collected in corresponding CRF form. Considering that, the time of the baseline subject symptom self-assessment during Day 1 (Visit 1) is used instead.
- It was specified by the protocol to compare the use of rescue medication with baseline. But according to the definition (see Section 5.1.7.4.2), there could not be a baseline rescue medication. Considering that, there is no comparison with baseline.
- It was specified by the protocol to conduct the eDiary Compliance summary in categories "<80%", "80%-100%" using frequency tables. But those are equal to the number of non-compliant (<80%) and compliant (80%-100%) subjects. Considering that, it was specified to present only the number of compliant and non-compliant subjects.

CONFIDENTIAL Page 25 of 30

Private and Confidential Study No LPS16453 Date: DEC 12, 2022

- It was specified by the protocol to use Intent-to-Treat population for Patch Use compliance analysis. In order to exclude non-treated subjects from analysis of treatment compliance, it is changed to Safety Population.
- It was specified by the protocol to use both Safety and Intent to Treat populations for eDiary Compliance analysis. Considering that there should be no major difference between those, it is decided to use only the Safety Population.
- It was specified by the protocol to analyze time-to-event endpoints by using Kaplan-Meier estimates for survival probabilities. Instead, those are analyzed with cumulative distributions by estimating cumulative incidence based on the Kaplan-Meier survival estimates. Log-Rank testing was kept without changes.

CONFIDENTIAL Page 26 of 30

6 APPENDIX

Appendix 1: Tables, Figures and Listings

Table Number	Table Title
14.1.1.1	Summary of Subject Disposition (All Enrolled)
14.1.1.2	Summary of Analysis Populations (All Randomized Subjects)
14.1.1.3	Summary of Protocol Deviations (Intent-to-Treat Population)
14.1.2.1	Summary of Demographic and Baseline Characteristics (Intent-to-Treat Population)
14.1.2.2	Summary of Demographic and Baseline Characteristics by Protocol Version < 4.0 and 4.0 (Intent-to- Treat Population)
14.1.3.1	Summary of Patch Application and Compliance (Safety Population)
14.1.3.2	Summary of eDiary Compliance (Safety Population)
14.1.3.3	Summary of Use of Rescue Medication (Safety Population)
14.1.3.4	Summary of Medications and Non-drug Treatments/Procedures received on Day 6 (Safety Population)
14.1.4	Summary of Medical History (Intent-to-Treat Population)
14.2.1.1	Summary of Pain Perception (Intent-to-Treat Population)
14.2.1.2	Summary of Pain Relief Score (Intent-to-Treat Population)
14.2.2.1	Primary Analysis of NRS-Response at Day 5 Visit 2 (Modified Intent-to-Treat Population)
14.2.2.2.1	Key Secondary Analysis of Normalized Sum of Pain Intensity Difference (Full Analysis Set)
14.2.2.2.2	Key Secondary Analysis of Mobility Evaluation (Full Analysis Set)
14.2.2.2.3	Key Secondary Analysis of Roland-Morris Disability Questionnaire Score (Full Analysis Set)
14.2.2.2.4	Key Secondary Analysis of Time (hours) to Reach Acceptable Pain (Full Analysis Set)
14.2.2.2.5	Key Secondary Analyses - Adjustments for Multiple Testing (Full Analysis Set)
14.2.2.2.6	Sensitivity Analysis of NRS-Response at Day 5 Visit 2 (Sensitivity Analysis Population)
14.2.2.3.1	Other Secondary Analysis of Time (hours) to Reach no Pain (Full Analysis Set)
14.2.2.3.2	Other Secondary Analysis of Time Course of PID (i.e. instantaneous pain NRS change from baseline) and Summary of Pain Perception (Full Analysis Set)
14.2.2.3.3	Other Secondary Analysis of Time Course of Pain Relief Summary of Pain Relief Score (Full Analysis Set)
14.2.2.3.4	Other Secondary Analysis of Normalized Sum of Pain Relief (Full Analysis Set)
14.2.2.3.5	Exploratory Analysis of Pain Perception – Average Pain, Worst Pain and Least Pain (Full Analysis Set)
14.3.1.1	Summary of Adverse Events (Safety Population)
14.3.1.2.1	Summary of Treatment-Emergent Adverse Events by System Organ Class and Preferred Term (Safety Population)
14.3.1.2.2	Summary of Unanticipated Adverse Device Effects by System Organ Class and Preferred Term for FIRTECH Patch Treatment Group (Safety Population)
14.3.1.2.3	Summary of Treatment-Emergent Adverse Events by System Organ Class, Preferred Term and by Severity (Safety Population)

CONFIDENTIAL Page 27 of 30

Table Number	Table Title
14.3.1.2.4	Summary of Treatment-Emergent Adverse Events by System Organ Class, Preferred Term and by
	Relationship (Safety Population)
14.3.1.2.5	Summary of Serious Treatment-Emergent Adverse Events by System Organ Class and Preferred Term
	(Safety Population)
14.3.5.1	Summary of Vital Signs (Safety Population)
14.3.5.2	Summary of Local Physical Examination (Safety Population)
14.3.6.1	Summary of Prior Medications (Safety Population)
14.3.6.2	Summary of Concomitant Medications (Safety Population)

CONFIDENTIAL Page 28 of 30

Figure Number	Figure Title
14.2.2.3.2	Other Secondary Analysis of Time Course of Pain Intensity Difference, Box Plots of Pain Intensity
	Difference (Full Analysis Set)
14.2.2.3.3	Other Secondary Analysis of Time Course of Pain Relief, Box Plots of Pain Relief (Full Analysis Set)
14.2.2.2.4	Cumulative Incidence Curve for Time (hours) to Reach Acceptable Pain (Intent-to-Treat Population)
14.2.2.3.1	Cumulative Incidence Curve for Time (hours) to Reach No Pain (Intent-to-Treat Population)

CONFIDENTIAL Page 29 of 30

Listing Number	Listing Title
16.1.7	Listing of Randomization (All Randomized Subjects)
16.2.1.1	Listing of Subject Disposition (All Subjects)
16.2.1.2	Listing of Screen Failure and Inclusion / Exclusion Criteria Assessment (All Subjects)
16.2.2	Listing of Protocol Deviations (All Subjects)
16.2.3.1	Listing of Analysis Populations (All Randomized Subjects)
16.2.3.2	Listing of Subjects Excluded from the Sensitivity Analysis Population (Modified Intent-to-Treat Population)
16.2.4.1	Listing of Subject Demographic and Baseline Characteristics (Intent-to-Treat Population)
16.2.4.2	Listing of Medical History (Intent-to-Treat Population)
16.2.4.3	Listing of Baseline Acute Low Back Pain History (Intent-to-Treat Population)
16.2.4.4.1	Listing of Prior Medications (Safety Population)
16.2.4.4.2	Listing of Concomitant Medications (Safety Population)
16.2.4.4.3	Listing of Use of Rescue Medication (Safety Population)
16.2.4.5	Listing of Non-drug Treatment/Procedure (Intent-to-Treat Population)
16.2.4.6	Listing of Medications and Non-drug Treatments/Procedures received on Day 6 (Safety Population)
16.2.5	Listing of Patch Application (Safety Population)
16.2.6.1.1	Listing of Pain Perception (Intent-to-Treat Population)
16.2.6.1.2	Listing of Roland-Morris Disability Questionnaire (Intent-to-Treat Population)
16.2.6.1.3	Listing of Mobility Evaluation (Intent-to-Treat Population)
16.2.6.2.1	Listing of Normalized Scores (Full Analysis Set)
16.2.6.2.2	Listing of Time-to-Event Evaluations (Full Analysis Set)
16.2.6.2.3	Listing of Instantaneous Pain NRS-Response at Day 5 Visit 2 (Modified Intent-to-Treat Population)
16.2.7	Listing of Adverse Events (All Subjects)
16.2.8	Listing of Pregnancy Test Results (Intent-to-Treat Population)
16.2.9.1	Listing of Vital Signs (Safety Population)
16.2.9.2	Listing of Local Physical Examination (Safety Population)
16.2.10	Listing of eDiaries Completion and Compliance (Safety Population)

CONFIDENTIAL Page 30 of 30

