The inferential analysis of time-to-event endpoints (time to reach acceptable pain, time to reach no pain) will include summary, display, and analysis using Kaplan-Meier estimation method. The comparison of survival distributions between the group with patch and no-patch group will be done by the Log-Rank test. During the analysis, if the event if interest never occurs, the time will be censored at the final visit.

These analyses will be based on the ITT population, using the ITT paradigm (i.e. as randomized).

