5.1.7.2 Key Secondary Analyses

Key Secondary analyses will be based on the FAS population.

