5.1.7.2.4 Time to Reach Acceptable Pain

Time to reach acceptable pain (TTAP) will be defined as the time (hours) from baseline subject symptom self-assessment date and time (Day 1 Visit 1, Pain Perception) to the first report of post-baseline acceptable pain. If that event never occurs, the time will be censored with the last response. If there are no post-baseline assessments collected, then the time will be censored with baseline subject symptom self-assessment.

TTAP will be listed and analyzed with cumulative distributions (F(t)) and the corresponding summaries using cumulative incidence estimates $(\hat{F}(t) = 1 - \hat{S}(t))$ based on the Kaplan-Meier survival estimates $(\hat{S}(t))$. The 95% confidence limits $(\hat{F}_L(t), \hat{F}_U(t))$ for point estimates will be evaluated using 95% confidence limits for survival estimates $(\hat{S}_L(t), \hat{S}_U(t))$ as follows:

$$\hat{F}_L(t) = 1 - \hat{S}_U(t); \ \hat{F}_U(t) = 1 - \hat{S}_L(t).$$

The comparison between treatment groups will be done by the Log-Rank test.

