5.1.7.3 Other Secondary Analyses

Other Secondary Analyses will be based on the FAS population.

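### The cumulative incidence figures for time to acceptable pain and time to no pain are titled ITT, but their tables, listing and log-rank tests use the FAS

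*SAP*

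**What the plan says.** The list of figures in SAP Appendix 1 contains two time-to-event figures:

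- Figure 14.2.2.2.4: "Cumulative Incidence Curve for Time (hours) to Reach Acceptable Pain (Intent-to-Treat Population".
- Figure 14.2.2.3.1: "Cumulative Incidence Curve for Time (hours) to Reach No Pain (Intent-to-Treat Population".

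The list of tables in the same appendix carries the same two numbers with a different population:

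- Table 14.2.2.2.4: "Key Secondary Analysis of Time (hours) to Reach Acceptable Pain (Full Analysis Set".
- Table 14.2.2.3.1: "Other Secondary Analysis of Time (hours) to Reach no Pain (Full Analysis Set".

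The SAP text agrees with the tables. Section 5.1.7.2 states "Key Secondary analyses will be based on the FAS population", and section 5.1.7.3 states "Other Secondary Analyses will be based on the FAS population". Time to acceptable pain is in the first section and time to no pain in the second. Both subsections end with the same instruction: "The comparison between treatment groups will be done by the Log-Rank test". Listing 16.2.6.2.2, which holds the event and censoring times, is also on the FAS.

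The protocol differs from the SAP text. In section 8.3.1.2, directly after the Kaplan-Meier and log-rank plan, it says "These analyses will be based on the ITT population, using the ITT paradigm (i.e. as randomized".

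**The concern.** A time-to-event figure and its log-rank test are normally read together: the curve shows the separation and the test says how surprising it is. Here the curve would keep everyone as randomized, while the test would come from a subset defined partly by what subjects did after randomization. Rescue use in an open-label trial with an untreated control may well depend on the assigned arm and on how the pain is going. Under the primary endpoint it is itself a form of non-response.

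Time to acceptable pain is a key secondary endpoint. It enters the Benjamini-Hochberg family, and SAP 5.1.7.2.5 allows confirmatory reading of that family if the primary endpoint is significant. The report should therefore make clear whose data support the claim.

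**Working it through.** **Step 1. The sources side by side**

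| Item | Acceptable pain | No pain |
|---|---|---|
| Protocol 8.3.1.2 | ITT | ITT |
| SAP text with the log-rank test | FAS (5.1.7.2) | FAS (5.1.7.3) |
| Table | FAS (14.2.2.2.4) | FAS (14.2.2.3.1) |
| Listing 16.2.6.2.2 | FAS | FAS |
| Figure | ITT (14.2.2.2.4) | ITT (14.2.2.3.1) |

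Within the SAP, only the figures stand apart. SAP 3.3 treats the summary, the survival curves and the Kaplan-Meier analysis as parts of one inferential analysis. Nothing calls the ITT curves supportive, and no ITT log-rank test is planned. The other two figures in the list, the box plots of pain intensity difference and pain relief, are on the FAS, so ITT is not a general rule for figures.

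**Step 2. How the two sets differ**

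SAP 4.1.1 defines ITT as everyone randomized. SAP 4.1.3 defines the FAS as ITT minus three groups:

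- subjects with rescue use from randomization to Day 5 Visit 2, or ongoing at randomization;
- subjects without a baseline NRS;
- subjects with a baseline instantaneous NRS of 0.

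Rescue is open to all subjects (protocol 6.4.4.3). SAP 5.1.7.4.2 defines it broadly, to include prohibited analgesics and non-drug therapy for pain.

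**Step 3. Number of subjects affected**

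The documents state no rescue rate, so there is no planned figure to reproduce. With 200 randomized and an assumed excluded fraction r, the FAS has 200 × (1 − r) subjects, and 200 × r are in the curve but not in the test.

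| r (assumed) | In curve only | FAS |
|---|---|---|
| 5% | 10 | 190 |
| 10% | 20 | 180 |
| 20% | 40 | 160 |
| 30% | 60 | 140 |
| 40% | 80 | 120 |

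**Step 4. Whether this can change a conclusion**

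This is a simulation on assumed inputs: 100 per arm; event hazard 0.012 per hour times a gamma frailty with mean 1; pain read every 12 hours to 96 hours; rescue likelier in subjects with slow response. The log-rank test was run on all subjects, and again after removing rescue users. Each row is 1,000 trials, except the first, which is 200.

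| Rescue, patch / control | Hazard ratio | p < 0.05, all | p < 0.05, rescue users removed | Opposite sides of 0.05 |
|---|---|---|---|---|
| 0% / 0% | 1.5 | 45.0% | 45.0% | 0% |
| 5% / 5% | 1.0 | 4.6% | 5.2% | 1.8% |
| 5% / 5% | 1.5 | 49.1% | 47.4% | 7.5% |
| 10% / 20% | 1.0 | 4.0% | 4.8% | 3.6% |
| 10% / 20% | 1.5 | 47.1% | 32.4% | 19.3% |
| 20% / 20% | 1.0 | 4.2% | 4.0% | 3.6% |
| 20% / 20% | 1.5 | 47.2% | 39.6% | 16.0% |
| 20% / 40% | 1.0 | 3.7% | 9.3% | 9.6% |
| 20% / 40% | 1.5 | 44.0% | 15.1% | 31.1% |

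With no exclusions the two p-values were identical in every run; with exclusions they never were. In the last row the mean difference in the proportion reaching the event by 96 hours was 11.0 percentage points in all subjects and 6.0 after exclusion. The curve would show the first and the p-value would reflect the second.

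**Step 5. Cases the ITT curve leaves undefined**

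The time origin for both endpoints is the baseline self-assessment (SAP 5.1.7.2.4 and 5.1.7.3.1), so a subject without one has no start time. Entry requires an NRS of at most 6 with no lower limit (protocol 6.4.5), and the SAP itself provides for a baseline of 0. The acceptable-pain definition requires a post-baseline report; the no-pain definition does not. Subjects with a baseline of 0 could thus count as events at time zero in the ITT curve.

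**Step 6. Declared changes**

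SAP 5.1.11 declares a new time origin and a new display for these two endpoints, and declares population changes for the compliance analyses. It does not mention the move from ITT to FAS, and it describes the log-rank testing as unchanged.

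**The case against.** The strongest reply is that the two figure titles are leftovers. The FAS entered the SAP only in version 3.0, the operative text assigns these analyses to it, and the table and listing follow. On that view a programmer would draw FAS curves and the correction is two words. This is plausible, but it is an inference. Version 4.0 revised both the FAS definition and the time-to-event analysis, the titles use that version's cumulative incidence wording, and they still say ITT. Retitling alone would also leave the departure from protocol 8.3.1.2 undeclared.

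A second reply is that an ITT curve could be a deliberate descriptive display. SAP 5.1.7.1 summarizes instantaneous pain on both ITT and FAS, and each title names its population. The documents do not show whether the p-value will be printed on the figure. This softens the risk of misreading. It does not explain why figure and table share a number, or why no ITT test accompanies an ITT curve.

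Two stronger readings are tempting. A reader might infer that the published curve will certainly contradict its p-value. The appendix lists outputs without saying what will be published, and the mismatch needs at least one randomized subject outside the FAS: very likely, since rescue is permitted, but not certain. A reader might also infer that a substantial share of the trial, say 40 to 80 of 200, is affected. That presumes 20% to 40% exclusion, for which the documents offer no basis; entry pain is at most 6 and subjects are told that rescue is not encouraged.

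It is also fair to object that simply moving everything to ITT is not a complete remedy. It would bring subjects with a baseline of 0 or no baseline into the test without a rule, and would affect the listing and the multiplicity table.

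**Conclusion.** The inconsistency is real and affects both time-to-event endpoints. Followed as written, the SAP pairs as-randomized curves with log-rank p-values from a subset selected partly on behaviour after randomization, and it moves the test away from the protocol's population without declaring this. That is more than a clerical slip, because one of the two endpoints can be read as confirmatory.

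The size is unknown. The range of 10 to 80 of 200 restates an assumed 5% to 40% exclusion. The simulated disagreement of about 8% to 31% at a hazard ratio of 1.5 depends on an assumed effect, assumed rescue rates and an assumed link between rescue and slow response. Both show that the choice of set can matter; neither predicts this trial. The point should be corrected before the outputs are produced.

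**What to change.** Use one population for each figure, its table, its listing and its log-rank test.

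**Preferred: the protocol's as-randomized set as the main analysis.**

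- Put Figures and Tables 14.2.2.2.4 and 14.2.2.3.1, Listing 16.2.6.2.2 and both tests on ITT.
- Keep the FAS as supportive, with its own curve.
- State in 5.1.7.3.1 that only post-baseline reports of NRS 0 count as events.
- State how subjects with a baseline NRS of 0, or with no baseline assessment, are handled for both endpoints.
- Update Table 14.2.2.2.5, now titled FAS, because time to acceptable pain would enter the multiplicity adjustment from a different set than the other three key secondary endpoints.

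**If the FAS is kept as the main set.**

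- Retitle both figures to FAS.
- Add a supportive ITT curve with its own log-rank p-value for each endpoint. The handling rules above are needed here too.
- Declare the move from ITT to FAS in 5.1.11, with the reason.

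The cost is a few extra outputs, label changes and some sentences in the SAP. No additional data are needed.
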